Our study will implement the caregiver survey and the medical record abstraction tools in the PFK ABD population. Caregivers of all 8,080 newly enrolled ABD children will be invited to participate in the survey. We estimate that our methods will yield 2,750 caregiver survey respondents. The estimated 34% response rate considers a combination of those who are unreachable based on available contact information and those who are reached but who opt out of participation. This sample size will allow us to estimate performance on each survey-based care coordination indicator within a 95% confidence interval of ± 1.5 percentage points (conservatively assuming underlying performance of 50%). Confidence interval widths for age, gender, and urban/rural subpopulations will range from ± 1.8 to ± 3.7 . This sample size will allow us to identify a significant urban/rural difference ($\alpha=0.05$) of 0.05 percentage points (i.e., 0.50 vs. 0.55) with a power of 0.83.

Medical Record Abstraction

Participants & Sample Size

We further estimate that 1,000 of those who complete the survey will consent to a review of their medical records that will allow data collection on medical record review based measures that can be linked to survey data and ultimately medical claims data. This consent rate is based on experience in current pilot work. This sample size will allow us to estimate performance on each medical record-based care coordination indicator within a 95% confidence interval of ± 2.9 percentage points (conservatively assuming underlying performance of 50%). Confidence interval widths for age, gender, and urban/rural subpopulations will range from ± 3.6 to 7.0. This sample size will allow us to identify a significant urban/rural difference ($\alpha=0.05$) of 0.10 percentage points (i.e., 0.50 vs. 0.60) with a power of 0.89.

Analysis

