ATTACHMENT B

Detailed Measure Specifications and Scoring for FECC Caregiver Survey Indicators

All are on 0-100 scale, where higher is better. Survey response items should be coded to reflect that. For dichotomous items, "no" = 0 and "yes" = 100. More specific instructions are included where applicable in Scoring Notes.

All screener items must be nonmissing for a dependent item to be scored

If items are part of a yes/no checklist, if at least one item is answered, impute "no" for skipped items in mailed surveys or "don't know" for telephone surveys (but not for items that telephone respondents refused to answer).

Otherwise, all component items must be nonmissing for a multi-item indicator to be scored.

MP=Main Provider

Indicator ID	Indicator Description	Eligible	Survey Item	Scoring notes
CARE COORDINATION SERVICES				
CC2	Caregivers should report that their child has a designated care coordinator.	Q2=1 (Child visited more than one doctor's office or used more than one kind of health care service in last 12 months)	Q3 (Someone in MP's office helped manage child's care or treatment from different doctors/providers)	
CC3	Caregivers who report that their child has a designated care coordinator (as identified in CC2) should report that they know how to access their care coordinator.	Q2=1 (Child visited more than one doctor's office or used more than one kind of health care service in last 12 months), Q3=1 (Someone in MP's office helped manage child's care or treatment from different doctors/providers)	Q6 (Knew how to contact person who helped manage child's care when you needed help or had a question)	
CC5	Caregivers who report having a designated care coordinator (as identified in CC2) and who require community services should also report that their care coordinator helped their child to obtain needed community services in the last year.	Q2=1 (Child visited more than one doctor's office or used more than one kind of health care service in last 12 months), Q3=1 (Someone in MP's office helped manage child's care or treatment from different doctors/providers), Q15=1 (Caregiver or child needed or used community services in last 12 mos)	Q16(Person in MP's office who helped manage child's care helped get community services)	

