CC7	Caregivers who report having a care coordinator (as identified in CC2) should also report that their care coordinator has contacted them (via face-to-face contact, telephone, email, or written correspondence) or attempted to contact them at least once in the last 3 months.	Q2=1 (Child visited more than one doctor's office or used more than one kind of health care service in last 12 months), Q3=1 (Someone in MP's office helped manage child's care or treatment from different doctors/providers)	Q7 (In last 3 mos, person contacted you w/o you getting in touch w/them first)
CC8	Caregivers of children with complex needs who report having a care coordinator and who report that their care coordinator has contacted them in the last 3 months should also report that their care coordinator asked them about the following:	Q2=1 (Child visited more than one doctor's office or used more than one kind of health care service in last 12 months), Q3=1 (Someone in MP's office helped manage child's care or treatment from different doctors/providers), Q7=1 (In last 3 mos, care coordinator contacted you w/o you getting in touch w/them first)	Mean of CC8a and CC8b
CC8a	Caregiver concerns	Q9 (Care coordinator asked about caregiver concerns)	
CC8b	Health changes of the child	Q10 (Care coordinator asked about health changes of child)	
CC8c	Caregivers who report the following: having a designated care coordinator, having a copy of a written shared care plan for their child, and having been contacted by their care coordinator in the last 3 months should also report that their care coordinator asked them about the following: Progress towards goals documented in the patient's shared care plan	Q2=1 (Child visited more than one doctor's office or used more than one kind of health care service in last 12 months), Q3=1 (Someone in MP's office helped manage child's care or treatment from different doctors/providers), Q7=1 (In last 3 mos, care coordinator contacted you w/o you getting in	Q31 (In last 12 mos, has MP or anyone from MP's office talked w/you about progress child was making toward goals written in shared care plan) If Q31=3 (Child's shared care plan does not have written goals), score as No

		touch w/them first), Q29=1 (MP created shared care plan for child), Q30=1 (Caregiver has copy of child's shared care plan)		

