IE3c	Was useful	Q20	
IE4	Caregivers should report having been invited to join in hospital rounds during their child's last hospitalization	Q21=1 (child had overnight hospital stay in last 12 mos)	Q25 (Last time child was in hospital, invited to take part in hospital rounds)
IE5	Caregivers/patients should report receiving a written visit summary of their child's last hospitalization at the time of discharge, and they should report the summary contained the following elements:	Q21=1 (child had overnight hospital stay in last 12 mos), Q22=1 (Last time child was in hospital, got written hospital stay summary at discharge)	Q23 (Did written hospital stay summary include...) Mean of IE5a-f
IE5a	Problem list at time of discharge	Q23a	
IE5b	Medication list at time of discharge	Q23b (Rx), Q23c (OTC)	Mean of rescaled Q23b and Q23c
IE5c	Drug allergies		Q23d (list of "child's allergies", not drug allergies specifically)
IE5d	Specialists involved in the child's care during the hospitalization		Q23e
IE5e	Planned follow-up		Q23f
IE5f	What to do for problems related to the hospitalization		Q23g
IE6	Caregivers who received a written summary of their child's hospitalization at discharge (as	Q21=1 (child had overnight hospital stay in last 12 mos), Q22=1 (Last time child was in	Q24 (Hospital stay summary easy to understand)

described in indicator IE5) should report that the information contained in the visit summary was easy to understand hospital, got written hospital stay summary at discharge)

MH3a	Caregivers should report having access to an electronic health record to look up information about their child's visits and health care.	All caregivers of children with medical complexity	Q26 (In last 12 mos, MP's office had web site or app caregiver could use between visits to look up information about child's visits and care)	If Q26=1 (Yes): 100 points If Q26=2 or 3 (No or Don't Know): 0 points
MH3b	Caregivers who report having access to an electronic health record should also report that it includes the following health information:		Q26=1 (In last 12 mos, MP's office had web site or app caregiver could use between visits to look up information about child's visits and care)	Do not score the N/A's; If no immunizations (meds), do not score MH3b1 (MH3b2); If didn't look at med list, do not score MH3b2 Take mean of MH3b1 and MH3b2

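### Aim 2 states ±1.5 points for each survey indicator, but that width at 50% performance needs about 96% of respondents scored, and Attachment B restricts eligibility for 17 of 20 indicators

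*Combined protocol and SAP*

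**What the plan says.** Combined protocol and SAP, Aim 2, Caregiver Survey, Participants & Sample Size: caregivers of all 8,080 children are invited and 2,750 are expected to respond (34%). On that basis the plan says it can "estimate performance on each survey-based care coordination indicator within a 95% confidence interval of ± 1.5 percentage points", with 50% performance as the conservative assumption. It allows wider intervals only for demographic groups: "Confidence interval widths for age, gender, and urban/rural subpopulations will range from ± 1.8 to ± 3.7". It then gives power for an urban/rural difference: "0.05 percentage points (i.e., 0.50 vs. 0.55) with a power of 0.83" (the example in brackets shows that five percentage points are meant).

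Attachment B gives each survey indicator its own Eligible rule. MH3a, SCP2 and SCP6 are open to "All caregivers of children with medical complexity". The others are screened. CC3, for example, is asked of "Caregivers who report that their child has a designated care coordinator (as identified in CC2"), and CC8 only of those "who report that their care coordinator has contacted them in the last 3 months".

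Aim 2, Analysis says that performance will be calculated on every care coordination measure and stratified by age group, urban/rural residence and type of disabling diagnosis.

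**The concern.** The precision statement covers *each* indicator and presents 50% performance as the cautious choice, so a reader takes ±1.5 as the widest margin to expect. The figure is computed on all respondents, whereas most indicators are scored only on those who pass one or more screens. The plan widens its intervals when a demographic split reduces the number, but not when an eligibility rule does the same.

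The items most exposed are those about the care coordinator's work, which is the subject of Aim 2. A reader who applies ±1.5 to them, or assumes that the urban/rural power carries over, may expect more precision than the design gives.

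**Working it through.** **Inputs from the documents.** n = 2,750 respondents, N = 8,080 children, performance 50%, 95% confidence (Aim 2, Caregiver Survey). Record-review sample 1,000, stated ±2.9 (Aim 2, Medical Record Abstraction). Eligibility rules from Attachment B.

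**1. Reproduce the plan's figure.**
- Without FPC: 1.96 × √(0.25/2,750) = 1.87 points, which is not ±1.5.
- FPC: √((8,080 − 2,750)/8,079) = 0.812. With it: 1.869 × 0.812 = 1.518, which rounds to ±1.5.
- Cross-check on 1,000 records: 3.10 without FPC, 2.90 with it, against ±2.9 stated.
- Cross-check on subgroups: ±1.8 implies (1.518/1.8)² = 71% of respondents with FPC, but (1.869/1.8)² = 108% without, which is impossible. ±3.7 implies (1.518/3.7)² = 17% with FPC.

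So the interval widths use an FPC with N = 8,080, and ±1.5 uses all 2,750 respondents.

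**2. Share that must be scored.** If a share f is scored and the eligible population shrinks in proportion, the half-width is 1.518/√f. It stays below 1.55, and so rounds to ±1.5, if f ≥ (1.518/1.55)² = 0.959, about 2,638 respondents. If N is held at 8,080, the share is 97.3% (2,675).

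**3. Who is scored.** Attachment B lists 20 indicators: CC2, CC3, CC5, CC7, CC8, CC8c, CC9, CC10, MH8, IE2 to IE6, MH3a, MH3b, MH6, SCP2, SCP4, SCP6. Three carry no screener item (MH3a, SCP2, SCP6), so 17 are screened.
- CC3, CC5, CC7, CC8c and CC9 are yes/no items that require Q3 = 1, a yes on CC2. CC5, CC8c and CC9 add further screens. At 50% performance they reach ±1.5 only if about 96% of respondents report a coordinator.
- SCP4 is yes/no and requires a child aged 15 or older. The study population is children up to age 18 (the section on handling missing data). ±1.5 at 50% would need about 96% of respondents' children to be 15 or older.

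**4. Size, as assumed scenarios.** The documents give no eligible shares. For a yes/no item at 50% with proportional FPC:

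| Share scored | n | Half-width |
|---|---|---|
| 90% | 2,475 | ±1.60 |
| 80% | 2,200 | ±1.70 |
| 50% | 1,375 | ±2.15 |
| 25% | 688 | ±3.03 |

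At 1,375 the half-width is ±2.41 with N held at 8,080 and ±2.64 without FPC. The 25% row would be the ceiling for CC8c if CC2 and CC7 were both 50%, before its care-plan screens.

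**5. What narrows the interval.**
- Performance away from 50%: the share needed is 0.959 × p(1 − p)/0.25, which is 61% at 20% or 80% performance and 35% at 10% or 90%.
- Averaged scores: CC8 is the "Mean of CC8a and CC8b". For two 50% items with correlation ρ the width is multiplied by √((1 + ρ)/2). At 1,375 this gives ±1.52 (ρ = 0) to ±2.15 (ρ = 1).

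**6. Power.** The urban/rural split behind 0.83 is not stated. A 71/29 split, inferred from ±1.8, gives 0.83 with FPC on 2,750. The same basis gives 0.87 for the record-review comparison (0.50 vs 0.60), where the plan states 0.89. A 50/50 split without FPC gives 0.89 there but 0.75 for the survey. Neither basis reproduces both figures.

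**The case against.** **The arithmetic is right.** This stands. ±1.5 reproduces for an indicator scored on all respondents. The fault is in the scope given to it.

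**No shortfall is shown for most of the 17.** This largely stands. A reader might infer that all 17 miss ±1.5. The documents do not support that, because they give no eligible shares. The screen for CC2 (more than one doctor's office or kind of service in the past year) may pass nearly everyone. Performance far from 50% or an averaged score also narrows the interval. But the plan chose 50% as its conservative case, and for the five coordinator items and SCP4 that case works only with about 96% eligible.

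**The 96% is a convention.** This is fair. It takes rounding as the criterion and a proportionally shrinking population. Holding N fixed makes it 97.3%, so the conclusion does not depend on the choice.

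**The scoring rule does not set denominators.** This stands. Attachment B also says "All screener items must be nonmissing for a dependent item to be scored". A reader might take that as the restriction, but it is a missing-data rule: a caregiver who answers no has a nonmissing screener. The Eligible column sets the denominator.

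**Even the three unscreened indicators may not cover everyone.** They refer to children with medical complexity, and the plan does not say that every respondent's child qualifies. The fix should therefore speak of indicators scored on essentially all respondents, without naming these three as certain.

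**Power of 0.83 was never claimed for each indicator.** This stands. A reader might conclude that 0.83 is wrong, or equally that it is confirmed. Step 6 supports neither.

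**Nothing in conduct changes.** This is true and limits the weight of the point. All caregivers are already invited, and final intervals will follow the number scored.

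**Conclusion.** The point holds in limited form. At the plan's own 50%, ±1.5 describes an indicator scored on about 96% or more of the 2,750 respondents, with an FPC that the plan does not state. It is not the conservative width for each indicator. The clearest cases are CC3, CC5, CC7, CC8c, CC9 and SCP4. The demographic subgroup widths rest on the same all-respondent base.

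The true size is unknown. It is negligible if nearly everyone is eligible, and the half-width would be about ±2.15 if half are. That 50% is a scenario, not a forecast of how many caregivers report a coordinator. The result assumes simple-proportion intervals and, for the quoted scenario widths, an FPC at the same sampling fraction. No estimate, test or recruitment target is affected, so this is a correction to stated design precision that should be made.

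**What to change.** In Aim 2, Caregiver Survey, Participants & Sample Size:

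1. Limit ±1.5, and the subgroup widths of ±1.8 to ±3.7, to indicators scored on essentially all respondents.
2. For screened indicators, give the half-width by eligible number as a range. For a yes/no item at 50% with FPC: ±1.70 at 2,200, ±2.15 at 1,375, ±3.03 at 688. Note that averaged scores, or performance far from 50%, can be narrower.
3. State that the interval widths use an FPC with N = 8,080.
4. Say that the power of 0.83 applies only to an indicator scored on all respondents, and state the urban/rural split and whether an FPC was used. Do not add detectable differences until the split is known, since they would rest on an assumed one.

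The cost is wording only, with no extra participants. The downside is that the stated figures look less favourable.

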 - CSRL will mail the follow-up letter to non-opt-out families with a web link and code. Participants will have one month to answer. After the month, CSRL will discontinue access to the web and then will know which part of the sample remaining to be called.
- Eligibility/Survey Administration
 - NCH will provide a summary of demographic data on opt-outs.
 - Families with more than 2 eligible patients – ask about the patient (i.e. child) for whom the interviewer is calling only.
 - Interviewer will ascertain which caregiver is the one who obtains health care/ the most involved in going to health care visits with the child and interview this person.
 - At end of survey, interviewer will confirm to whom the check should be mailed and confirm mailing address – participant can choose any person to send check to.
 - We will add 'Yes I agree, No I don't agree' for consent box at the end of survey – this will serve as documentation that interviewer obtained verbal consent.
- Reporting
 - CSRL will provide weekly reports on calls that will include such information as: bad numbers, number called, number ineligible, those we haven't screened, screened but declined, and completed, and medical record consents. May also include how long the interview has taken and profiling.

Timeframe

March 1 UNC provide CSRL with all IRB-approved materials, including consent

materials, screener, and the survey in both English and Spanish.

March 27	CSRL send web-based survey link for pilot testing with the patient advisory panel.
March 27- April 5	Patient advisory panel members pilot the web-based survey.
April 6	Quarterly Advisory Panel Meeting – investigators solicit PAP input including such things as need for more instructions, navigation issues, using the interface (do links work, etc.), is survey user-friendly.
April 10	UNC provide feedback about the web-based survey to CSRL
May 1	PFK mail out opt-out letters.
May 31	Preliminary demographics due to PCORI (prepared by NCH).
June 9	End of 40-day period.
June 23	NCH send eligible sample to CSRL.
July 1	Begin web survey. CSRL send follow-up letters to eligible sample with code and web address.
July 31	End date for web survey.
August 1	Begin telephone survey.
October 31	End date for telephone survey.
Nov 30	CSRL send final dataset to UNC.

Medical Record Review

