Based on our pilot work, we expect that 1,000 caregivers who complete the phone survey will also provide consent for abstraction of their medical records for MR based care coordination measures. Data for Medical record-based care coordination measures will be collected primarily through review of the Epic EMR at Nationwide Children’s Hospital (NCH) conducted by an experienced, trained NCH abstractor using a field-tested data abstraction tool. The integrated EMR at NCH allows review of NCH inpatient visits and primary and specialty care services provided by physicians in the NCH system. We estimate 50% of ABD children enrolled in PFK were seen in the NCH system in the past year. If a participant lists a main provider outside of the NCH system, a copy of the relevant medical records will be requested from that provider for review. The first 20 records will be re-reviewed by a second abstractor for quality control and training.

Aim 3

Assumptions

- PFK data and claims data are housed on servers at NCH.

- NCH has permission from PFK to use data.
- NCH has permission from the state to use data.
- NCH will provide a limited de-identified dataset at the person-month level.
- Data will be provided in SAS and STATA format.
- Data will be available for download from a secure server using a double-password system.
- [name], [name], [name], [name], and the NCH programmer will have access to the data.

Steps for Data Preparation and Access

1. [name] and [name] will develop a programming guide for the programmer.
2. NCH Programmer links PFK and state data (EHR data, claims data) to study data (caregiver data) and strips identifiers.
3. NCH Programmer creates an analytic file.
4. NCH Programmer runs frequencies.
5. NCH Programmer makes de-identified dataset available in both SAS and Stata formats.
6. NCH will notify team that data are available for download.
7. [name] will log on to server using double-password system (VPN-like system).
8. [name] will download and house data on secure site at UNC & OSU.

Dissemination Plan

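### Aim 2 urban/rural powers and comparisons make no allowance for shared main-provider offices or siblings, so standard errors can be too small if offices sit mostly within one residence stratum

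*Combined protocol and SAP*

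**What the plan says.** Under Aim 2, Caregiver Survey, the sampling unit is the child: "Caregivers of all 8,080 newly enrolled ABD children will be invited to participate in the survey". The expected yield follows: "We estimate that our methods will yield 2,750 caregiver survey respondents". The section then states: "This sample size will allow us to identify a significant urban/rural difference", at alpha 0.05, and gives power 0.83 for 0.50 versus 0.55. The Medical Record Abstraction section gives 0.89 for 0.50 versus 0.60 with 1,000 records. Neither states an ICC, a cluster count or a design effect.

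The Aim 2 Analysis section stratifies indicators by urban/rural residence and links them to claims outcomes. It names no test and no variance method. Generalized estimating equations are named only for the Aim 3 outcome models, with no clustering unit.

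Attachment B lists 20 top-level survey indicators, counting CC8c and MH3b separately. Seventeen score what the main provider's office, or its care coordinator, did or has. MH3a, for example, asks whether the "MP's office had web site or app caregiver could use between visits to look up information about child's visits and care". The other three (IE4 to IE6) concern the last hospital stay.

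On families, the survey's Key Decisions say: "Families with more than 2 eligible patients – ask about the patient (i.e. child) for whom the interviewer is calling only". This limits what one interview covers. It does not limit a family to one record, and read literally it does not reach a family with exactly two eligible children.

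**The concern.** Children who attend the same office can be expected to have correlated answers on items about that office, strongly so for a portal and less so for a care plan written for one child. Two children of one caregiver can be correlated as well. When such records are treated as independent, the variance of a between-office contrast is understated. If residence largely follows the office, the urban/rural contrast is of that kind.

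Two things are at stake. The promised powers may be optimistic, and a nominal 5% test may reject too often. Both would carry into statements about whether coordination is equal across subpopulations, and into the linked analyses when the exposure is a feature of the office. The sections on projected use and dissemination intend the findings for other health systems and ACOs, so inference beyond this population is part of the purpose.

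**Working it through.** **Inputs from the documents.** 8,080 children; 2,750 survey respondents (34%); 1,000 record reviews; alpha 0.05; powers 0.83 and 0.89; 95% half-widths of ±1.5 and ±2.9 points at 50%. The urban/rural split and the sidedness of the test are not stated.

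**Step 1: reproduce the plan's figures.**

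- Half-widths. Without a finite population correction (FPC), 98/√2,750 = 1.87 and 98/√1,000 = 3.10. With it, 1.87 × √(1 − 2,750/8,080) = 1.52 and 3.10 × √(1 − 1,000/8,080) = 2.90. The stated intervals therefore include an FPC.
- Survey power (normal approximation, two proportions). Two-sided without FPC gives at most 0.747, at a 50/50 split. One-sided 50/50 without FPC gives 0.837. Two-sided with FPC gives 0.835 at 29/71 and 0.843 at 30/70.
- Record-review power. Two-sided with FPC at 30/70 gives 0.877. Two-sided without FPC at 50/50 gives 0.890.

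The best common account is two-sided with FPC at about 30/70. Both powers are thus reproduced without any design effect.

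**Step 2: survey, offices nested in residence strata.** Respondents per office (m) and ICC are assumptions, because the documents give neither. Formulas:

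- Design effect DE = 1 + (m − 1) × ICC
- True type I error = 2 × [1 − Φ(1.96/√DE)]
- Revised power = Φ((z + 1.96)/√DE − 1.96), where z = 0.954 for a stated power of 0.83 and 1.227 for 0.89

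| m | ICC | DE | Type I error | 0.83 becomes |
|---|---|---|---|---|
| 5 | 0.02 | 1.08 | 0.059 | 0.80 |
| 5 | 0.05 | 1.20 | 0.074 | 0.76 |
| 10 | 0.02 | 1.18 | 0.071 | 0.77 |
| 10 | 0.05 | 1.45 | 0.104 | 0.68 |
| 20 | 0.02 | 1.38 | 0.095 | 0.70 |
| 20 | 0.05 | 1.95 | 0.160 | 0.55 |

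Worked row (m = 10, ICC 0.05): DE = 1 + 9 × 0.05 = 1.45 and √1.45 = 1.204. Then 1.96/1.204 = 1.628, so type I error is 0.104. Also (0.954 + 1.96)/1.204 − 1.96 = 0.460, so power is 0.68.

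**Step 3: record review on the same offices.** Cluster size shrinks by 1,000/2,750 = 0.364, so 5, 10 and 20 become 1.8, 3.6 and 7.3. At m = 1.8 and ICC 0.02, DE = 1.02 and 0.89 stays at about 0.89. At m = 3.6 and ICC 0.05, DE = 1.13 and power is 0.85. At m = 7.3 and ICC 0.05, DE = 1.31 and power is 0.79. Attachment B covers only the survey, so it is a further assumption that record-based measures cluster by office to the same degree.

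**Step 4: siblings only.** With 1.05 to 1.2 records per family and ICC 0.5 (assumed), DE is 1.03 to 1.10, type I error is 0.053 to 0.062, and 0.83 becomes 0.82 to 0.79.

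**Step 5: offices fully crossed with residence.** The variance of the difference is about (1 − ICC) times the independent value. Type I error is then 0.048 at ICC 0.02 and 0.044 at ICC 0.05, so p-values would be slightly too large.

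**Step 6: linked regressions.** The inflation is about 1 + (m − 1) × ICC(exposure) × ICC(outcome). At m = 20 with both at 0.05 it is 1 + 19 × 0.0025 = 1.05. For an exposure that is identical within an office (ICC 1) it is 1 + 19 × 0.05 = 1.95.

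**The case against.** **Direction.** A reader might infer that the urban/rural p-values are definitely too small. The documents do not show this. Residence is recorded for the child, and nothing says that offices are wholly urban or wholly rural. The Medical Record Review section says "We estimate 50% of ABD children enrolled in PFK were seen in the NCH system in the past year", which makes mixed offices plausible. Step 5 then applies. This part of the objection stands.

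**Target population.** The FPC in the intervals points to inference about these 8,080 children, who are all invited individually. For describing them, office clustering adds no sampling design effect. This also stands. It does not settle the matter, because the stated uses go beyond this ACO. For that wider target the FPC falls away, and two-sided power is at most 0.747 even before clustering.

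**Silence.** The plan does not say that children will be treated as independent; it names no Aim 2 test at all. That is correct, but an unspecified variance method for a promised significance test is itself a gap.

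**Size.** A reader might divide half the respondents by the hospital's 68 facilities (1,375/68 = 20.2), add an ICC of 0.10, and arrive at DE 2.9, a type I error of 25% and survey power of 0.40. The 68 facilities include urgent care, research and specialty sites, and being seen in the system is not the same as having one's main provider there. Many indicators also apply only to eligible subsets, which makes clusters smaller. Nor can survey design effects be carried over to record review. DE 2.9 would give 0.47 there, whereas 7.3 records per office at the same ICC gives DE 1.63 and power 0.70.

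**Content.** Not every office item is shared by all children of the office. School contact or a care plan for one child can vary within it.

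**Conclusion.** The point holds in conditional form. The plan's urban/rural powers contain no design effect, and no clustered variance is planned for Aim 2, although most survey indicators describe an office and families can contribute more than one record. Standard errors can be too small if three things are true together: the ICC is positive, offices lie mostly within one residence stratum, and the inference reaches beyond these 8,080 children. Under 5 to 20 respondents per office, ICC 0.02 to 0.05 and full nesting, all assumed, type I error is about 6% to 16%. Survey power falls from 0.83 to about 0.80 to 0.55, and record-review power from 0.89 to about 0.89 to 0.79. The effect of siblings alone is small.

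The documents do not support saying that the p-values will be wrong in a known direction, or by a known amount. The change is still worth making, because clustered variance is appropriate whichever way the offices divide.

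**What to change.** 1. Attach a coded main-provider practice identifier (from the survey, where the participant names the provider, or from claims) and a coded household identifier to each record. Create both before the hospital's programmer strips identifiers.
2. Name the Aim 2 test. Use practice-clustered variance for the urban/rural tests and linked regressions, with household nested within practice, or two-way clustering if siblings attend different practices.
3. Reword the multi-child rule so that it covers families with two or more eligible children, and say whether more than one record per family is accepted.
4. Restate both powers over a range of ICCs and cluster sizes. Give the assumed urban/rural split and the sidedness, and say whether an FPC is used and hence which population the inference concerns.

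The cost is a small amount of linkage work and a cluster option in the analysis code, with no new data collection if claims supply the practice. The downside is that the stated powers become somewhat less favourable.
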